**Baseline Definition:**

- The table below provides baseline definition for the endpoints to be analyzed. If the endpoint doesn't have assessment except at Day 1 (such as PRO) then baseline will be Day 1 value
- High/Low/Normal will be derived for baseline values, calculated as the mean of all pre-treatment results, based on the ULN and LLN.
- Subjects with repeated baseline: For the purpose of change from baseline, if the subject has a repeated baseline after IP re-challenge, change from baseline will be based on the 1st baseline value

**Baseline Definition**

[figure not shown]
Assessment	Baseline Definition
Serum Chemistry, Hematology and Coagulation	The mean of all available evaluations prior to the first administration of investigational product.
Lipoprotein	The last fasted assessment prior to the first administration of investigational product
Markers of glucose metabolism	The last fasted assessment prior to the first administration of investigational product
Cardiovascular Assessment	The last assessment prior to the first administration of investigational product
ECG	The mean of all available evaluations prior to the first administration of investigational product.
Anthropometric measures	The mean of all available evaluations prior to the first administration of investigational product
Vital signs	The mean of all available evaluations prior to the first administration of investigational product
Exploratory Biomarkers	The mean of all available evaluations prior to the first administration of investigational product.

[figure not shown]
Pharmacodynamic Parameters	The mean of all available evaluations prior to the first administration of investigational product.
----------------------------	---

### Additional Conventions:

1. Normal reference ranges may change during the study due to assays re-validated with new reference ranges. For example, reference ranges used in the 747-303 study including INR, APT, APPT, Bicarbonate have been updated during the study.
  - INR, APT, and PPT: Changes in normal reference ranges were implemented to reflect appropriate ranges based on collected data overtime. The update in reference ranges does not reflect changes in sample analysis and consequently the same value corresponding to reference ranges should be considered the same. The latest reference range will be used in summaries. In listings, reference ranges will be reported as received from ICON lab.
2. Concomitant medications:
  - Use of CMSCAT and CMCLASCD versus ATC (level 2, level 4) for hypertensive medications and diabetic medications along with indication.
3. AEs: SMQ
  - Hepatic disorder: Hepatic Disorders SMQ, excluding the following sub-SMQs: congenital, familial, neonatal and genetic disorders of the liver; Liver infections; alcohol related sub SMQ as one of the excluded sub SMQ, and Pregnancy-related hepatic disorders.
  - Cardiac events: the MedDRA Broad SMQs of embolic and thrombotic events or Ischemic heart disease, or Central nervous system vascular disorders narrow SMQ.
  - Renal AEs: Renal Standardized MedDRA query (SMQ): acute renal failure, chronic kidney disease, proteinuria, renovascular disorders, or tubulointerstitial diseases
  - Dyslipidemia: Dyslipidemia SMQ
  - Gallbladder Disease and Related Complications: Gallbladder Related Disorders narrow SMQ and Gallstone Related disorders narrow SMQ, with additional PTs of Biliary abscess, Biliary sepsis, Biliary tract infection, Gallbladder abscess, Gallbladder empyema, Bile duct necrosis, Bile duct obstruction, Bile duct stenosis, Biliary colic, Cholangitis, Cholangitis acute, Cholangitis chronic, Cholecystocholangitis, and Perforation bile duct.
  - Pancreatitis: Acute Pancreatitis narrow SMQ
  - Hyperglycemia: Hyperglycaemia/new onset diabetes mellitus narrow SMQ
4. CTCAE Clarifications:
  - CTCAE for PH is based on blood test and not urine test

- CTCAE for glucose depends on fasting glucose test for grade 1-2 and any available glucose test (fasting or non-fasting) for grade 3-4.
- Lab units in CTCAE grade derivation: Values in SI values will be used to derive CTCAE classification

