15.1.7. Potential Liver-Related Clinical Outcome Events

Specified liver-related clinical outcome events may, by definition (see [Section 15.1.1.3](#)) qualify as SAEs. The Sponsor must be notified of any SAEs within 24 hours of the site becoming aware of the event (see [Section 15.1.6.2](#)). The Sponsor is responsible for regulatory reporting of SAEs, including expeditious reporting of SUSARs, refer to [Section 15.1.2](#) for definition of SUSAR.

Given that the liver-related clinical outcome events could also meet the criteria of a SUSAR, which would necessitate unblinding for expedited reporting, the Sponsor will not expeditiously report potential liver-related clinical outcome events in order to retain the study blind and preserve the integrity of the clinical outcomes endpoint. These events will be selected as a

“study event” on the Adverse Event CRF and will be submitted for adjudication to the Hepatic Outcomes Committee as described in [Section 16.11](#).

The Sponsor will consider the following list of clinical outcome events (MedDRA preferred terms) to be disease related and exempt from expeditious regulatory reporting, but will continue to report them in a non-expeditious manner: death, end-stage liver disease (preferred term: chronic hepatic failure), liver transplant (preferred term: liver transplant), [REDACTED], [REDACTED], variceal bleeding (preferred terms: gastroesophageal variceal haemorrhage, esophageal varices haemorrhage), hepatic encephalopathy (preferred term: hepatic encephalopathy), spontaneous bacterial peritonitis (preferred term: peritonitis bacterial), ascites secondary to cirrhosis (preferred term: ascites), and progression to cirrhosis (preferred term: hepatic cirrhosis).

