#### **10.4.2. Hepatic Safety Analysis**

Hepatic disorders are different and separate from primary efficacy endpoint of hepatic clinical outcomes and are defined as events included in the Hepatic Disorders SMQ, excluding the following sub-SMQs: alcohol related; congenital, familial, neonatal and genetic disorders of the liver; liver infections; and pregnancy-related hepatic disorders.

Summaries will include overall summary of hepatic disorder TEAEs, summary of the incidence of hepatic disorder TEAEs, related TEAEs, TEAEs with CTCAE Grade 3 or higher, TEAEs

leading to treatment discontinuation, TEAEs leading to study discontinuation, SAEs, TEAEs leading to death.

In order to explore the relationship between hepatic disorders and OCA, the following time-to-event analyses will be performed:

- EAIR of custom hepatic queries for PTs “Acute hepatic failure” (hepatic failure) and “Ammonia increased” (hepatic injury)
- Incidence of hepatic TEAEs by PT, and baseline fibrosis status
- Incidence of hepatic SAEs by PT, and baseline fibrosis status

Potential drug induced liver injury (DILI) Triggers: Potential cases of DILI in Study 747-303 are identified via a set of biochemical, adverse event (SMQ based) and study visit questionnaire triggers. These cases then undergo clinical review by the Hepatic Safety Adjudication Committee (HSAC) of all available data for each identified subject to determine liver injury status (including causality and severity).

Summary tables for identified cases will present frequencies of triggers by treatment group as well as highest causality and severity association.

Additional DILI analyses will include the following:

- EAIR of DILI cases adjudicated for ALL cases of hepatic injury by severity and treatment arms
- EAIR of DILI cases adjudicated as  $\geq$  possible causality and severity injury by treatment arms
- Incidence of potential DILI by baseline weight (<85kg, 85-100 kg, and >100 kg)
- Incidence of potential DILI by baseline BMI (<30 kg/m^2,  $\geq$ 30 kg/m^2 to <35 kg/m^2,  $\geq$ 35 kg/m^2)
- Incidence of potential DILI by use of known hepatotoxic medications prior to the event
- Incidence of potential DILI by baseline fibrosis using histology based on original eligibility baseline fibrosis stage.
- Time to onset of first occurrence of adjudicated DILI (Possible, Prob, Highly Likely causality AND  $\geq$  Moderate severity)

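### The SAP calls its hepatic adverse-event category separate from the primary liver outcomes, but the definition removes none of those outcomes, so the pooled hepatic AESI results could mix disease progression with liver injury

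*SAP*

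**What the plan says.** SAP 10.4.2 makes the claim of separation and gives the definition in one sentence: "Hepatic disorders are different and separate from primary efficacy endpoint of hepatic clinical outcomes and are defined as events included in the Hepatic Disorders SMQ". The exclusions that follow are "alcohol related; congenital, familial, neonatal and genetic disorders of the liver; liver infections; and pregnancy-related hepatic disorders". SAP Appendix A (Additional Conventions, item 3) repeats the same four: "Hepatic disorder: Hepatic Disorders SMQ, excluding the following sub-SMQs: congenital, familial, neonatal and genetic disorders of the liver; Liver infections", with "alcohol related sub SMQ as one of the excluded sub SMQ, and Pregnancy-related hepatic disorders".

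Protocol 15.1.7 says how outcome events are recorded. They are marked as a study event "on the Adverse Event CRF and will be submitted for adjudication to the Hepatic Outcomes Committee". The section lists their MedDRA preferred terms, among them chronic hepatic failure, hepatic encephalopathy and variceal haemorrhage terms, and "ascites secondary to cirrhosis (preferred term: ascites), and progression to cirrhosis (preferred term: hepatic cirrhosis". SAP 6.4.7.1 dates the ascites component from its adverse-event start date, so one record serves both efficacy and safety.

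SAP 10.3 defines a TEAE as an event from randomization to 30 days after the last dose. SAP 10.4 then asks, for each AESI category, for incidence overall and by preferred term, EAIR differences with 95% CIs for the category and for each term, and Kaplan-Meier curves to the first event and to the first severe or serious event. None of these sections removes records that carry the study-event flag.

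**The concern.** If the hepatic category were disjoint from the primary outcomes, some rule would have to take the outcome records out. The four exclusions concern other causes of liver disease; none concerns cirrhosis, decompensation or adjudicated events. A subject who progresses to cirrhosis or develops ascites on treatment therefore appears to count in the efficacy analysis and also in the hepatic AESI category.

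This matters for any result that pools hepatic terms. If OCA slows progression, fewer progression events on OCA pull the pooled comparison in its favour, and an excess of other liver events on OCA would look smaller than it is. Protocol 5.5 already describes liver safety in pooled terms, reporting similar overall hepatic TEAEs but more serious ones on 25 mg. That does not show dilution, but it shows that the pooled row is read.

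**Working it through.** **Comparison of the texts.** Four questions settle the definition.

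1. Are outcome events in the adverse-event data? Yes (Protocol 15.1.7).
2. Do they carry liver terms? Several do: hepatic cirrhosis, hepatic encephalopathy, chronic hepatic failure, ascites, variceal haemorrhage.
3. Does the hepatic query exclude them? Not through any of the four listed sub-queries.
4. Does another rule exclude them? None is stated in SAP 10.3, 10.4 or 10.4.2.

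The documents do not list the contents of the Hepatic Disorders SMQ, so the exact overlap cannot be confirmed from them.

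**Illustration of size.** The documents give no figure to reproduce.

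- From SAP 2.2.1: 288 outcome events in placebo plus OCA 25 mg, and 2085 stage 2 or 3 subjects randomized 1:1:1, so 2085 / 3 = 695 per arm.
- Assumed: the hazard ratio (the available text shows no design value); the share f of outcomes captured as hepatic TEAEs; a 5% background of other hepatic events on placebo; and a true excess of 4.0 points in those other events on OCA 25 mg.

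The placebo cumulative hazard H solves

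695(1 − exp(−H)) + 695(1 − exp(−HR × H)) = 288.

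At HR 0.70 this gives 167 + 121 = 288 events, or 24.0% against 17.5%, a difference of 6.5 points. To a first approximation the pooled difference shifts by f × 6.5 points: 1.6 at f = 0.25, 3.3 at f = 0.5, 6.5 at f = 1.

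Counting each subject once and treating the two kinds of event as independent, the pooled proportion is 1 − (1 − f × outcome proportion)(1 − other hepatic proportion). At HR 0.70 and f = 0.5:

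- placebo: 1 − (1 − 0.120)(0.95) = 16.4%
- OCA 25 mg: 1 − (1 − 0.0875)(0.91) = 16.9 to 17.0%, depending on rounding
- difference: +0.6 points, where the true excess is +4.0

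| Assumed HR | Outcomes, placebo vs OCA 25 mg | Shown at f = 0.25 | f = 0.5 | f = 1 |
|---|---|---|---|---|
| 0.6 | 25.3% vs 16.1% | +1.6 | −0.7 | −5.4 |
| 0.7 | 24.0% vs 17.5% | +2.3 | +0.6 | −2.9 |
| 0.8 | 22.8% vs 18.7% | +2.8 | +1.7 | −0.6 |
| 1.0 | 20.7% vs 20.7% | +3.8 | +3.6 | +3.2 |

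Each entry in the last three columns is the pooled difference, in points, when the true excess is +4.0. A 10% background moves an entry by at most about 0.4 points. At HR 1.0 progression offsets nothing; the small loss arises because a subject with both kinds of event counts once. The calculation covers crude incidence only. The EAIR and Kaplan-Meier versions were not computed.

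**The case against.** A reader might infer that a benefit on progression would hide drug-induced liver injury from the hepatic safety tables in general. The documents do not support that, for four reasons.

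- AESI incidence and EAIR are also given by preferred term, so a row for cirrhosis or ascites leaves the rows for other hepatic terms untouched.
- SAP 10.4.2 adds DILI analyses adjudicated by the HSAC, by causality and severity, and Protocol 16.9.2 keeps that adjudication apart from outcome adjudication. SMQ-based adverse events help to find cases, but the committee then reviews each one.
- SAP 10.5.4 adds eDISH plots and biochemical triggers, which rest on laboratory values.
- SAP 10 plans no inferential safety comparison unless specified.

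The overlap may also be partial. Death from any cause, MELD of 15 or more and transplant are not shown to fall in the query. Outcomes count after treatment stops (SAP 2.3.2.1), whereas TEAEs end 30 days after the last dose. Against this, Protocol 7.1 keeps subjects with an outcome event on product unless a discontinuation criterion is met, and SAP 10.4 also asks for overall AESI incidence during the study. The share captured is unknown, not negligible.

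The separation sentence could be read as conceptual: the AESI category is simply not the adjudicated endpoint. That reading is possible, but the same sentence supplies the operational definition, and a programmer is left without an instruction on flagged records.

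The most substantial point concerns the remedy. Protocol 5.5 reports 9 hepatic decompensation SUSARs, described by signs that largely match the components of the primary endpoint. Decompensation is itself a safety concern, and nothing in the documents says that confirmation by the Hepatic Outcomes Committee rules out a drug cause. Keeping these events in a safety table is defensible. This stands, and it argues for showing both versions.

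**Conclusion.** The definition does not deliver the separation that SAP 10.4.2 states. The pooled hepatic AESI outputs (overall incidence, category-level EAIR difference, and Kaplan-Meier time to the first and to the first severe or serious event) could mix progression outcomes with other hepatic events. A benefit on progression could then dilute or offset an excess of liver injury in those rows and curves.

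The size rests on assumptions. Full offset needs a real progression benefit, a substantial captured share, and an excess of other liver events smaller than the pull. At an assumed HR of 0.70 and a 5% background, the excess that would be fully cancelled is 1.6 points at f = 0.25, 3.4 at f = 0.5 and 7.5 at f = 1. A reader might also expect serious dilution with no efficacy effect, by thinking of a relative risk. The planned between-arm measure here is the EAIR difference, and in the crude-incidence illustration at HR 1.0 a true +4.0 still shows as +3.2 to +3.8.

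The point is therefore confined to the pooled outputs. It is worth correcting before unblinding, and it does not leave the plan blind to drug-induced liver injury.

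**What to change.** In SAP 10.4.2 and Appendix A, specify the pooled hepatic AESI incidence, EAIR and Kaplan-Meier outputs in two versions: all hepatic events, and the same with study-event records confirmed by the Hepatic Outcomes Committee removed. Present them side by side, with neither replacing the other. Reword the separation sentence to say what each version contains.

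The flag and the adjudication result are already collected, so the cost is SAP wording and a second run of existing tables and curves. The drawback is that a decompensation caused by the drug would appear only in the all-events version, which is why both must be shown.

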## APPENDIX C. PREFERRED TERMS TO IDENTIFY POTENTIAL KIDNEY INJURY

**Table C1: Preferred Terms (List 1)**

Acute kidney injury
Acute phosphate nephropathy
Acute prerenal failure
Anuria
Cardiorenal syndrome
Continuous haemodiafiltration
Crush syndrome
Crystal nephropathy
Haemolytic uremic syndrome
Hepatorenal failure
Nephritis
Nephropathy toxic
Pancreatorenal syndrome
Postoperative renal failure
Postrenal failure
Prerenal failure
Renal failure acute
Renal injury
Renal ischemia
Renal tubular injury
Renal tubular necrosis
Traumatic anuria
Tubulointerstitial nephritis
Urate nephropathy
Urine output decreased

**Table C2: Preferred Terms (List 2)**

Azotemia
Blood creatinine abnormal
Blood creatinine increased
Blood urea increased
Blood urea nitrogen/creatinine ratio increased
Creatinine renal clearance abnormal
Creatinine renal clearance decreased
Dialysis
Glomerular filtration rate abnormal
Glomerular filtration rate decreased
Haemodialysis
Haemofiltration
Hypercreatinemia
Hypercreatininemia
Metabolic nephropathy
Neonatal anuria
Oedema due to renal disease
Renal disorder
Renal failure
Renal failure neonatal
Renal function test abnormal
Renal impairment
Renal insufficiency
Renal tubular disorder
Renal tubular dysfunction
Subacute kidney injury
Urea renal clearance decreased
Urinary tract toxicity

### APPENDIX D. LIVER LABORATORY CRITERIA FOR MONITORING FOR POTENTIAL HEPATIC INJURY

Baseline	Treatment Emergent	Signs and Symptoms of Hepatic Injury a	Action
ALT Normal/Near Normal b	ALT $\geq 5x$ ULN TB normal Gilbert's c : no change in BL TB	No	
 
Repeat laboratory testing including CPK within 2-4 days
 

	ALT $\geq 3x$ ULN Regardless of TB or DB	Yes	
Interrupt
 
 
Repeat laboratory testing including CPK within 2-4 days
 
Collect PK sample within 7 days
 

	ALT $\geq 8x$ ULN Regardless of TB or DB	No	
Interrupt
 
 
Repeat laboratory testing including CPK within 2-4 days
 
Collect PK sample within 7 days
 

	ALT $\geq 3x$ ULN TB $\geq 2x$ ULN Gilbert's c : DB $\geq 2x$ ULN or INR $>1.5$	No	
Interrupt
 
 
Repeat laboratory testing including CPK within 2-4 days
 
Collect PK sample within 7 days
 

ALT Elevated b	ALT $\geq 3x$ BL or $\geq 300$ U/L, whichever occurs first TB normal Gilbert's c : no change from BL TB	No	
 
Repeat laboratory testing including CPK within 2-4 days
 

	ALT $\geq 2x$ BL or $\geq 300$ U/L, whichever occurs first Regardless of TB or DB	Yes	
Interrupt
 
 
Repeat laboratory testing including CPK within 2-4 days
 
Collect PK sample within 7 days
 

	ALT $\geq 5x$ BL or $\geq 500$ U/L, whichever occurs first Regardless of TB or DB	No	
Interrupt
 
 
Repeat laboratory testing including CPK within 2-4 days
 
Collect PK sample within 7 days
 

	ALT $\geq 2x$ BL or $\geq 300$ U/L, whichever occurs first TB $\geq 2x$ ULN Gilbert's c : DB $>2x$ ULN or INR $>1.5$	No	
Interrupt
 
 
Repeat laboratory testing including CPK within 2-4 days
 
Collect PK sample within 7 days
 

TB ( $>1.5$ mg/dL exclusion criterion 747-303)	TB $\geq 2.0$ mg/dL and DB $>30\%$ of TB	Yes/No	
Interrupt
 
 
Repeat laboratory testing including CPK within 2-4 days
 
Collect PK sample within 7 days
 

Baseline	Treatment Emergent	Signs and Symptoms of Hepatic Injury a	Action
ALP ≤ULN d	ALP ≥2x BL and >ULN	No	
If ALP <250 U/L, then:
 
 
Repeat laboratory testing including CPK within 2-4 days
 
 
If ALP ≥250 U/L, then:
 
Interrupt
 
 
Repeat laboratory testing including CPK within 2-4 days
 
Collect PK sample within 7 days
 

		Yes	
Interrupt
 
 
Repeat laboratory testing including CPK within 2-4 days
 
Collect PK sample within 7 days
 

ALP >ULN d	ALP ≥2x BL or >300 U/L, whichever occurs first	No	
If ALP <300 U/L, then:
 
 
Repeat laboratory testing including CPK within 2-4 days
 
 
If ALP ≥300 U/L, then:
 
Interrupt
 
 
Repeat laboratory testing including CPK within 2-4 days
 
Collect PK sample within 7 days
 

		Yes	
Interrupt
 
 
Repeat laboratory testing including CPK within 2-4 days
 
Collect PK sample within 7 days
 

ALP = alkaline phosphatase; ALT = alanine aminotransferase; BL = baseline; DB = direct bilirubin; CPK = creatine phosphokinase; DILI = drug-induced liver injury; INR = international normalized ratio; NASH = nonalcoholic steatohepatitis; OCA = obeticholic acid; PK = pharmacokinetic; TB = total bilirubin; ULN = upper limit of normal

a Signs and symptoms of hepatic injury include severe fatigue, nausea, vomiting, right upper quadrant pain, fever, rash, and eosinophilia.

b Baseline ALT is defined as an average of all pre-treatment values from Screening and Day 1. Elevated Baseline defined as ALT ≥1.5x ULN. ALT decreases are common within the first 3-6 months of treatment in NASH subjects receiving OCA. If there is a decrease in ALT for all lab draws through the Month 6 Visit, then a new baseline should be established for subsequent DILI determination, based on the average ALT from the Month 3 and Month 6 Visits.

c A subject will be considered to have Gilbert's syndrome if it was established at baseline and documented in the subject's medical history.

d Baseline ALP is defined as an average of all pre-treatment values from Screening and Day 1. Modest ALP increases (<50%) from baseline within the first 3 months of treatment are common in NASH subjects receiving OCA and represent an expected pharmacodynamic effect. If there is an increase in ALP through the Month 6 Visit, then a new baseline should be established for subsequent DILI determination, based on the average ALP from the Month 3 and Month 6 Visits.
